5.5. Subject and Study Completion

A complete subject is one who has completed both treatment periods, all assessments up to Day 35 of both treatment periods, and all of the follow-up assessments.

The end of the study is defined as the last subject's last visit.

6. STUDY TREATMENT

6.1. Investigational Product

The term 'study treatment' is used throughout the protocol to describe any combination of products received by the subject as per the protocol design. Study treatment may therefore refer to the individual study treatments or the combination of those study treatments.

| | Study Treatment | |
|---|---|--|
| Product name: | FF/Vilanterol Inhalation Powder , 100/25 mcg per blister | Placebo To Match FF/Vilanterol Inhalation Powder |
| Formulation description: | First strip: FF blended with lactose, 100 mcg per blister Second strip: Vilanterol blended with lactose and magnesium stearate ¹ , 25 mcg per blister ² | First strip: lactose Second strip: lactose and magnesium stearate ¹ |
| Dosage form: | Dry Powder Inhaler | Dry Powder Inhaler |
| Unit dose strength(s)/Dose level(s): | FF/Vilanterol 100/25 mcg ² | N/A |
| Route of Administration/ Duration: | Inhaled/ Taken once a day for 14 ± 2 days | Inhaled/Taken once a day for 14 ± 2 days |
| Dosing instructions: | 1 inhalation | 1 inhalation |
| Physical description: | Dry powder Inhaler | |
| Manufacturer/ source of procurement: | GSK | GSK |

1. Magnesium stearate 1% w/w of total drug product

2. 40 mcg of Vilanterol trifenate (triphenylacetate salt) is equivalent to 25 mcg of Vilanterol (free base).

6.2. Treatment Assignment

Subjects will be assigned to one of two treatment sequences (AB or BA, where A is placebo and B is FF/VI 100/25 mcg) in accordance with the randomization schedule generated by Clinical Statistics, prior to the start of the study, using validated internal software.

If more than 4 subjects prematurely discontinue the study, these subjects may be replaced at the discretion of the Sponsor, in consultation with the investigator. A replacement subject would be assigned to the same treatment sequence as the original withdrawn subject.

6.3. Blinding

This will be a double-blind study and the following will apply.

- The investigator or treating physician may unblind a subject's treatment assignment **only in the case of an emergency OR in the event of a serious medical condition when knowledge of the study treatment is essential for the appropriate clinical management or welfare of the subject as judged by the investigator.**
- Investigators have direct access to the subject's individual study treatment.
- It is preferred (but not required) that the investigator first contacts the Medical Monitor or appropriate GSK study personnel to discuss options **before** unblinding the subject's treatment assignment.
- If GSK personnel are not contacted before the unblinding, the investigator must notify GSK as soon as possible after unblinding, but without revealing the treatment assignment of the unblinded subject, unless that information is important for the safety of subjects currently in the study.
- The date and reason for the unblinding must be fully documented in the CRF.

The patients, site staff and GSK will remain blinded for the duration of the study.

A subject will be withdrawn if the subject's treatment code is unblinded by the investigator or treating physician. The primary reason for discontinuation (the event or condition which led to the unblinding) will be recorded in the CRF.

- GSK's Global Clinical Safety and Pharmacovigilance (GCSP) staff may unblind the treatment assignment for any subject with an SAE. If the SAE requires that an expedited regulatory report be sent to one or more regulatory agencies, a copy of the report, identifying the subject's treatment assignment, may be sent to investigators in accordance with local regulations and/or GSK policy.

Sealed code break envelopes will be provided to the site, in case of unblinding.

6.4. Packaging and Labeling

The contents of the label will be in accordance with all applicable regulatory requirements.

6.5. Preparation/Handling/Storage/Accountability

No special preparation of study treatment is required.

- Only subjects enrolled in the study may receive study treatment and only authorized site staff may supply or administer study treatment. All study treatments must be stored in a secure environmentally controlled and monitored (manual or automated) area in accordance with the labelled storage conditions with access limited to the investigator and authorized site staff.

- The investigator, institution, or the head of the medical institution (where applicable) is responsible for study treatment accountability, reconciliation, and record maintenance (i.e. receipt, reconciliation and final disposition records).
- Further guidance and information for final disposition of unused study treatment are provided in the SRM.
- Under normal conditions of handling and administration, study treatment is not expected to pose significant safety risks to site staff. Take adequate precautions to avoid direct eye or skin contact and the generation of aerosols or mists. In the case of unintentional occupational exposure notify the monitor, Medical Monitor and/or GSK study contact.
- A Material Safety Data Sheet (MSDS)/equivalent document describing occupational hazards and recommended handling precautions either will be provided to the investigator, where this is required by local laws, or is available upon request from GSK.

6.6. Compliance with Study Treatment Administration

When subjects are dosed at the site (on Day 1 and Day 14 of each treatment period), they will receive study treatment directly from the investigator or designee, under medical supervision. The date and time of each dose administered in the clinic will be recorded in the source documents. The dose of study treatment and study subject identification will be confirmed at the time of dosing by a member of the study site staff other than the person administering the study treatment.

When subjects self-administer study treatment at home (on Days 2 to 13 of each treatment period), dosing details will be completed by the subjects in individual paper diaries, and then later transcribed by the site into the CRF. Dosing compliance will be assessed through querying the subject during the subsequent site visits and this will be documented in the source documents and CRF. A dosing record for each subject must be maintained and reconciled with study treatment and compliance records.

Subject compliance with study treatment administered at home will be reinforced by the site using various methods including the use of daily text reminders and weekly telephone contact. More details will be given in the SRM.

6.7. Treatment of Study Treatment Overdose

An overdose for this study will be considered as any dose of study drug more than the planned dose on each dosing occasion. In the event of an overdose, there are no recommended medications or non-drug therapies for treatment. GSK is not recommending specific treatment guidelines for overdose and toxicity management. The investigator should contact the GSK Medical Monitor, and is advised to refer to the relevant documents for detailed information regarding warnings, precautions, contraindications, adverse events, and other significant data pertaining to the study drug(s) being used in this study. Such documents may include, but not limited to, the Investigator's Brochure (IB) or equivalent document provided by GSK, the approved product label if applicable, or both. Clinical judgment should be used in treating the

overdose. Management should be supportive and the investigator should use his/her clinical judgement in treating any overdose situation. Subjects experiencing such adverse events will be followed up clinically until the event has resolved.

6.8. Treatment after the End of the Study

Subjects will not receive any additional treatment from GSK after completion of the study because the indication being studied is not life threatening or seriously debilitating and/or other treatment options are available.

The investigator is responsible for ensuring that consideration has been given to the post-study care of the subject's medical condition, whether or not GSK is providing specific post-study treatment.

6.9. Lifestyle and/or Dietary Restrictions

6.9.1. Meals and Dietary Restrictions

6.9.1.1. Nitrate-rich foods

Nitrate-rich foods should be avoided as much as possible from Day -7 throughout the duration of the study until completion of the follow-up visit. Details of nitrate-rich foods are given in the table below:

| Nitrate-rich Food* |
|--------------------|
| Beetroot |
| Celery |
| Cabbage |
| Aubergine |
| Spinach |
| Radish |
| Broccoli |
| Cauliflower |
| Carrot |
| Lettuce |
| Radish |
| Turnip/swede |

*Vegetables such as beetroot, celery, lettuce, radishes and spinach contribute about 85 to 90% of an adult's dietary intake of nitrate, with nitrate levels ranging from 1700 to 2400 mg/kg food [Vints, 2005]. This food should be avoided as much as possible for the duration of the study. Specially prepared food will be given to the subjects whilst in-clinic and subjects will be reminded about this restriction for all other periods.

6.9.1.2. Caffeine and Alcohol

- From the screening visit until the follow up visit, subjects must not drink more than the equivalent of 4 standard cups of coffee/tea per day (e.g. 4 single shot cups or 2

double shot cups) and they must not drink more than 2 standard alcoholic drinks per day (e.g. 2 standard glasses of wine, where a standard glass = 175 mL).

- Subjects must abstain completely from coffee, tea, and alcohol within 2 hours of any of the lung function measurements.

6.9.2. Activity

Patients should avoid rigorous exercise for at least 2 hours before each FeNO and lung function measurement.

6.10. Concomitant Medications and Non-Drug Therapies

6.10.1. Permitted Medications and Non-Drug Therapies

6.10.1.1. Permitted asthma medications

The current asthma therapy for the patients enrolled in this study will be Short-Acting Beta2-Agonists (SABA), and patients must have been prescribed SABA for at least 12 weeks prior to screening.

6.10.1.2. Other permitted medications

Regarding subjects with any upper respiratory disorders including allergic rhinitis (both seasonal and perennial) and chronic rhinosinusitis (with or without nasal polyps), any subject who is on chronic maintenance therapies for these conditions will continue on their current standard of care medications (i.e. intranasal corticosteroids, antihistamines, cromones) throughout the entire duration of the study.

6.10.2. Prohibited Medications and Non-Drug Therapies

6.10.2.1. Prohibited asthma medications

Inhaled corticosteroids (ICS), long acting beta agonists (LABA), leukotriene receptor antagonists (LTRA), long acting muscarinic antagonists (LAMA), oral steroids, omalizumab (Xolair) and mepolizumab (Nucala) are prohibited from 3 months prior to the start of the study until after the study follow-up visit.

6.10.2.2. Prohibited non-asthma medications

The following medications may not be used during the study from first dosing to the end of Treatment Period 2 inclusive:

- Anticonvulsants (barbiturates, hydantoins, and carbamazepine)
- Polycyclic antidepressants
- β -adrenergic blocking agents
- Nonsteroidal anti-inflammatory drugs (NSAIDs)
- Phenothiazines

- Monoamine oxidase (MAO) inhibitors

7. STUDY ASSESSMENTS AND PROCEDURES

Protocol waivers or exemptions are not allowed with the exception of immediate safety concerns. Therefore, adherence to the study design requirements, including those specified in the Time and Events Table, are essential and required for study conduct.

This section lists the procedures and parameters of each planned study assessment. The exact timing of each assessment is listed in the Time and Events Table Section [7.1](#).

Additional detailed procedures for obtaining each assessment are provided in the Study Reference Manual (SRM) where specified.

The timing and number of planned study assessments, including safety and spirometry assessments may be altered during the course of the study to ensure appropriate monitoring. The change in timing or addition of time points for any planned study assessments must be approved and documented by GSK, but this will not constitute a protocol amendment. The Institutional Review Board (IRB)/Independent Ethics Committee (IEC) will be informed of any safety issues that require alteration of the safety monitoring scheme.

A subject may attend an unscheduled visit at any time if the investigator deems necessary for safety reasons.

7.1. Time and Events Table

| Procedure | Screening (up to 42 days prior to Day 1) | Study Day (each treatment period) | | | | | | Follow-up (Days 35- 42) ¹³ | Notes |
|---|---|---|----------------|---------------|----------------|-----------|-----------|---|--|
| | | Day -7 (start of run-in) ¹ | Day 1 | Days 2- 13 | Days 14-19 | Day 21 | Day 35 | | |
| Out-patient visit to the unit | X | X | X | | | X | X | X | ¹ Day -7 is the start of the one week run-in period and therefore this visit and the assessments on this day only apply to Treatment Period 1 |
| Admission to the unit | | | | | X | | | | |
| Informed consent | X | | | | | | | | |
| Inhaler, PEF meter and FeNO device practice | X | | | | | | | | |
| Inclusion and exclusion criteria/eligibility review | X | X | X ² | | | | | | ² Treatment Period 1 only |
| Demography | X | | | | | | | | |
| Full physical exam including height and weight | X | | | | | | | | |
| Medical history (includes substance usage [and family history of premature CV disease]) | X | | | | | | | | Substances: [Drugs, Alcohol, tobacco and caffeine] |
| Past and current medical conditions [including cardiovascular medical history] | X | | | | | | | | |
| Urine pregnancy test (WCBP) | X | | X ³ | | | X | | X | ³ Collected pre-dose |
| Vital signs | X | | | | | | | | |
| Set up PEF and FeNO monitoring | | X | | | | | | | |
| Study Treatment | | | X ⁴ | | X ⁵ | | | | ⁴ Dosing every morning; dosing in the unit on Days 1 and 14 and at home on Days 2-13 ⁵ Dosing on the morning of Day 14 only |

| Procedure | Screening (up to 42 days prior to Day 1) | Study Day (each treatment period) | | | | | | Follow-up (Days 35- 42) ¹³ | Notes |
|---|---|---|----------------|---------------|----------------|-----------------|-----------------|---|---|
| | | Day -7 (start of run-in) ¹ | Day 1 | Days 2- 13 | Days 14-19 | Day 21 | Day 35 | | |
| Exploratory biomarker sampling ⁶ | | | X | | X | X | X | | ⁶ These measurements are taken at baseline (Day 1 pre-dose), at the end of treatment (Day 15), on Day 21 and on Day 35. |
| FEV ₁ readings ⁷ | X | | X ⁸ | | X ⁹ | X ¹⁰ | X ¹⁰ | | ⁷ Measured in the unit only ⁸ Taken pre-dose ⁹ Collected AM (pre-dose on Day 14) and PM ¹⁰ Collected AM only |
| FeNO assessment ¹¹ | X | ←=====→ | | | | | | | ¹¹ Start of collection 7 days before Day 1 (Day -7), then collected every day AM and PM through to Day 35 of each treatment period. |
| PEF ¹² | | ←=====→ | | | | | | | ¹² Collected AM and PM every day from Day -7 through to Day 35 for Treatment Period 1, and from Day 1 through to follow up for Treatment Period 2. |
| AE/SAE review | | ←=====→ | | | | | | | |
| Concomitant medication review | | ←=====→ | | | | | | | ¹³ Follow up visit only after Treatment period 2. The follow-up visit can be combined with the Day 35 visit for Treatment Period 2. |
| Issue of diary card | X | | | | | X ¹⁴ | | | ¹⁴ Second diary card given out on Day 21 of Treatment Period 1, to capture data for Treatment Period 2 |

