PEF measurements (best of 3 recordings) will be recorded AM and PM (i.e. every 12 hours) from Day-7 through to Day 35 of Treatment Period 1, and then from Day 1 of Treatment Period 2 through to the follow-up visit. Subjects will be provided with a PEF meter and these measurements will be captured electronically whilst they are at home and in the clinic.

Treatment Arms and Duration

Each subject will participate in two treatment periods of 14 (\pm 2 days). FF/VI 100/25 mcg will be received once daily (AM dosing) in one period and placebo (AM dosing) will be administered in the other period. At the end of each treatment period, there will be a monitoring period of 21 days.

Total duration for each subject (from screening to follow-up) will be a minimum of 76 days, with a maximum of up to 21 weeks, depending on the screening period and the time period between Treatment Periods 1 and 2.

A complete subject is one who has completed both treatment periods, all assessments up to Day 35 of both treatment periods, and all of the follow-up assessments.

Type and Number of Subjects

Approximately 28 adult subjects with asthma will be enrolled into this study to ensure that 24 subjects complete dosing and critical assessments for both treatment periods.

Analysis

Following \log_e -transformation, primary endpoint of FeNO change from baseline ratio following cessation of treatment will be analyzed using a mixed effects repeated measures model with fixed effect terms for period, treatment, day, time, (period-level baseline)*day*time interaction term, treatment*day*time interaction term, period-level baseline and subject-level baseline. Day*time interaction term will be fitted as repeated measure.

Secondary endpoints of FeNO change from baseline ratio during treatment and FEV₁ will be analysed similarly to the primary FeNO endpoint. FEV₁ will not be log-transformed.

PEF and safety data will be listed and summarised. Exploratory biomarker data (including blood eosinophil and serum periostin data) will be summarized descriptively, if available.

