4. STUDY DESIGN

4.1. Overall Design

This study will be a randomised, double blind, placebo-controlled, two-period, crossover repeat dose study in adult subjects with asthma.

Following screening, subjects will provide AM and PM FeNO and PEF data from Day -7 of Treatment Period 1. The Day -7 AM FeNO readings will be used to confirm eligibility (FeNO >40ppb). On Day 1, pre-treatment (AM) FeNO, FEV₁ and PEF readings will be used as baseline for Treatment Period 1. Subjects will then receive FF/VI 100/25 or placebo once daily (AM) for 14 (\pm 2) days. All treatments will be taken at the same time of day (within \pm 2 hours of the treatment on Day 1).

FeNO will be measured by the subjects AM (pre-dose) and PM for 14 days during each treatment period. On Day 14, FEV₁ and FeNO will be recorded before the final dose of FF/VI or placebo.

FeNO (AM and PM) will be measured for 21 days after the end of treatment (up to Day 35 for each of the two treatment periods). This will be as an in-patient on Days 14 to 19. All FeNO (out-patient and in clinic) measurements will be obtained using the same FeNO meter for each subject.

FEV₁ will be recorded AM and PM (i.e. every 12 hours) as an in-patient on Days 14 to 19. Subjects will then be discharged before returning 2 days later (on Day 21) for a further measurement of FEV₁ (168 hours post-treatment). An FEV₁ measurement will also be performed on Day 35.

Up to 4 weeks after the final assessment is collected on Day 35 of Treatment Period 1, subjects will then be crossed over to the alternative treatment. Baseline FEV₁, PEF and FeNO values will be collected pre-treatment in the morning on Day 1: these will be the baseline values for Treatment Period 2. Subjects will then receive FF/VI 100/25 or placebo once daily (AM) for 14 (\pm 2) days. The second treatment period procedures will be identical to the first treatment period.

[figure not shown]
A single measurement of FeNO will be collected according to ATS/ERS guidelines at each time point, using a NIOX Vero device with electronic data capture. Appropriate dietary and/or lifestyle restrictions will be applied. The order of assessments collected in the clinic will be: FeNO, FEV₁, and then PEF. When the subjects are at home, FeNO will be collected before the PEF measurements. FEV₁ measurements taken within 6 hours of SABA use will not be analysed.

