4.2. Treatment Arms and Duration

Each subject will participate in two treatment periods of 14 (\pm 2 days). FF/VI 100/25 mcg will be received once daily (AM dosing) in one period and placebo (AM dosing) will be administered in the other period. At the end of each treatment period, there will be a monitoring period of 21 days. At the end of this monitoring period following Treatment Period 1, there may be a period of up to a further 4 weeks before the subjects start Treatment Period 2.

A schematic is shown below:

Total duration for each subject (from screening to follow-up) will be a minimum of 76 days, with a maximum of up to 21 weeks, depending on the screening period and the time period between Treatment Periods 1 and 2. The screening visit can be combined with the Day -7 visit if convenient. Likewise, if no gap is required between Treatment Period 1 and Treatment Period 2, the Day 35 visit for Treatment Period 1 can be combined with the Day 1 visit of Treatment Period 2.

A complete subject is one who has completed both treatment periods, all assessments up to Day 35 of both treatment periods, and all of the follow-up assessments.

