4.4. Design Justification

Treatment period. The characterisation of the FeNO time profile following administration of FF is not known and its determination is the primary objective of this study. The onset of action of ICS on FeNO occurs within a few days with significant and near maximal effects seen after one week. In subjects with asthma and elevated FeNO (mean baseline eNO >65ppb) treatment with FP for 5 days reduced FeNO by 47-60% with a similar effect produced across a 40-fold dose range (50-2,000 mcg twice daily (BD); GSK Document Number [GM2005/00525/00](#)). A lesser reduction of approximately 33% from baseline was seen with FP 1,000 mcg BD for 3 days [GSK Document Number [GM2003/00418/00](#)] suggesting that this treatment duration may have been sub-optimal. Approximately 90% of the maximal effect of mometasone furoate on FeNO was seen after 7 days treatment compared with 14 days treatment (Nolte, 2013) These data suggest that the selected treatment period of 14 days should be associated with a near maximal effect of FF on eNO and that a longer treatment duration would be unlikely to result in further substantial effects.

Washout. As the duration of action of FF on eNO is not known, the washout period of at least 21 days represents a pragmatic balance between a likely duration of action and successful and timely study completion. A washout period of 14-28 days was successfully used in a previous study with repeat dose FP [GSK Document Number [GM2005/00525/00](#)]. There is a minimum of a 21 day washout period from the end of Treatment Period 1 to the start of Treatment Period 2. This is expected to be a sufficient washout for FeNO levels to return to baseline. However, to provide flexible scheduling for Treatment Period 2, there may be a further period of up to 4 weeks after the end of this initial 21 day washout period has finished before the subject commences Treatment Period 2.

Design Rationale. A placebo-controlled double-blind crossover study is preferred to a parallel group as this will require fewer subjects. Screening failure rates in a similar study [GSK Document Number [2014N194756_00](#)] at the same site were in the order of 90% and a parallel group study is not considered to be feasible. The drop-out rate predicted for this study is considered to be low (based on the previous study HZA116592 conducted at the same site) [GSK Document Number [2014N194756_00](#)].

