4.6.1. Risk Assessment

| Potential Risk of Clinical Significance | Mitigation Strategy | Monitoring implemented |
|--|---|---|
| Investigational Product (IP) | | |
| There is a potential risk of worsening asthma as subjects will receive placebo in one treatment arm and no treatments during the washout periods (however access to SABA rescue medication will be available throughout the entire study). | Stopping criteria will be applied for both FEV ₁ (during the clinic stays/visits) and PEF (out-patient and in-clinic) which will be monitored throughout the study treatment and washout periods. | Stopping criteria will be applied for both FEV ₁ (during the clinic stays) and PEF (out-patient and in-clinic) which will be monitored throughout the study treatment and washout periods. |
| As with any inhaled medication paradoxical bronchospasm may occur with an immediate wheeze after dosing. | If bronchospasm occurs following dosing, immediate administration of a short-acting (i.e., quick relief) inhaled bronchodilator (e.g., albuterol) is recommended. If this treatment fails to provide relief, a physician should be contacted immediately and/or emergency treatment should be sought. | First dose of the study medication in each treatment period will be administered in the clinic under the supervision of a physician. |
| FF/VI is contraindicated in subjects with severe milk protein allergy or known hypersensitivity or any ingredient of the preparation. | These subjects will be excluded from the study. | Not applicable. |
| Cardiovascular effects, such as cardiac arrhythmias e.g. supraventricular tachycardia and extrasystoles may be seen with sympathomimetic drugs, including fluticasone furoate/vilanterol. Therefore fluticasone furoate/vilanterol should be used with caution in patients with severe cardiovascular disease. | Caution is needed in patients with pre-existing cardiovascular (CV) disease, especially severe CV disease. Patients with severe CV disease will be excluded. | Not applicable |

| Potential Risk of Clinical Significance | Mitigation Strategy | Monitoring implemented |
|---|--|---|
| Investigational Product (IP) | | |

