7.3.3. PEF

Each subject will be given a PEF meter by the site on Day -7. Data will be captured electronically.

Subjects must measure morning and evening PEF as indicated in the time and events table. Three technically acceptable PEF measurements will be collected at each time point and the highest values will be recorded.

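### No PEF is scheduled in the optional gap of up to four weeks between periods, although the risk section says PEF is monitored throughout washout

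*Protocol*

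**What the plan says.** **PEF schedule.** The Protocol synopsis and 4.1 schedule PEF "from Day-7 through to Day 35 of Treatment Period 1, and then from Day 1 of Treatment Period 2 through to the follow-up visit". Time and Events note 12 gives the same two blocks, "Collected AM and PM every day from Day -7 through to Day 35 for Treatment Period 1, and from Day 1 through to follow up" (the latter in Period 2), and SAP Appendix 3 note 11 repeats it. Section 7.3.3 ties home readings to that table: "Subjects must measure morning and evening PEF as indicated in the time and events table". The table shows no visit and no FEV1 between Period 1 Day 35 and Period 2 Day 1.

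**Length of the gap.** Section 4.1 places the crossover "Up to 4 weeks after the final assessment is collected on Day 35 of Treatment Period 1". Section 4.4 says "there may be a further period of up to 4 weeks after the end of this initial 21 day washout period has finished". Section 4.2 lets the two visits be combined "if no gap is required between Treatment Period 1 and Treatment Period 2".

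**Monitoring commitment.** Section 4.6.1 names worsening asthma on placebo and during untreated washout as a risk. Its mitigation is stopping criteria on clinic FEV1 and on "PEF (out-patient and in-clinic) which will be monitored throughout the study treatment and washout periods".

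**Meaning of washout.** Section 4.4 says: "There is a minimum of a 21 day washout period from the end of Treatment Period 1 to the start of Treatment Period 2".

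**The concern.** Section 5.4 withdraws a subject whose PEF is below the stability limit on at least four consecutive days, and 7.3.3.1 keeps that limit in force for the rest of the study and sets the meter to alert on it. Both need readings. A site that follows the schedule asks for none in the gap, so the rule still applies but has no scheduled data to act on.

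The hazard named in 4.6.1 does not end at Day 35. Subjects are still without study treatment, and 6.10.2.1 still prohibits other controller therapy. A fall in PEF without heavy rescue use or an exacerbation could go unnoticed until the clinic measurements before dosing on Period 2 Day 1. By contrast, after Period 2 the plan continues PEF beyond Day 35 to follow-up.

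What is at stake is safety monitoring and agreement between a written mitigation and the schedule meant to deliver it. PEF is only listed and summarised, so no model or confidence interval depends on this.

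**Working it through.** **Inputs.** Screening up to 42 days before Day 1, run-in from Day -7 and follow-up on Days 35 to 42 (Protocol 7.1); each period runs to Day 35; gap of up to 4 weeks (4.1, 4.4); treatment nominally 14 days; last dose on Day 14.

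**Step 1: reproduce the stated durations (4.2: 76 days to 21 weeks).**
- Minimum, visits combined: 7 + 35 + 35 − 1 = 76 days. This matches with a gap of 0.
- Maximum: 42 + 35 + 28 + 35 + 7 = 147 days = 21 weeks. This matches with a gap of 28 days.

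On nominal 14-day treatment, the stated maximum therefore includes a full four-week gap. With the permitted ±2 days the sum is not unique: if monitoring shifts with the last dose, two 16-day treatment periods give 42 + 37 + 24 + 37 + 7 = 147. That does not matter here, because 4.1 and 4.4 allow the four weeks outright.

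**Step 2: days with no scheduled PEF.**
- 4.1 wording: Period 2 Day 1 falls at most 28 days after Day 35, leaving 27 whole days between (Days 36 to 62). 27 × 2 = 54 readings.
- 4.4 wording: up to four full weeks between, so 28 days. 28 × 2 = 56 readings.
- Combined visits: 0.

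**Step 3: share of off-treatment days before Period 2.** Days 15 to 35 are 21 covered days, so for a gap of g days the share is g / (21 + g).

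| Gap g (days) | Off-treatment days | Share with no scheduled PEF |
|---|---|---|
| 0 | 21 | 0% |
| 7 | 28 | 25% |
| 14 | 35 | 40% |
| 21 | 42 | 50% |
| 27 (4.1 maximum) | 48 | 56% |
| 28 (4.4 maximum) | 49 | 57% |

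**Step 4: the four-day rule.** A gap of g days contains g − 3 complete four-day windows: 27 − 3 = 24 or 28 − 3 = 25 at the maximum. Scheduled readings cover none of them.

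**Step 5: is the gap washout?**
- For: 4.4 calls 21 days a minimum and measures washout to the start of Period 2. Section 7.3.2.2 also keeps the Period 1 FEV1 limit as the reference until the Period 2 pre-dose time point.
- Against: 4.4 also places the extra weeks after an initial 21-day washout has finished, and the SAP 2.3 design diagram shows a 21-day washout. The word initial fits either reading, since it can imply that more washout follows.

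The balance favours the first reading without settling it.

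**The case against.** The strongest reply is that washout means Days 15 to 35 only. PEF is then recorded twice daily throughout washout, 4.6.1 is met, and what remains is loose wording. That reading is possible, so this is not a certain contradiction. It does not remove the practical point, though: subjects are equally untreated in the gap, and the PEF limit still applies.

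A second reply is that the stake is small. Much of this stands:
- Subjects entered on rescue bronchodilator alone, with no inhaled steroid or other controller for three months (5.1), so the gap returns them to their usual therapy.
- They reach it after 21 days of off-treatment PEF and a Day 35 clinic FEV1.
- The criteria in 5.4 on rescue use, severe exacerbation and investigator judgement need no PEF.
- Adverse events are collected throughout, and unscheduled visits are allowed (section 7).
- A voluntary reading below the limit should prompt contact with the site (7.3.3.2).
- Clinic PEF and FEV1 are taken before the first Period 2 dose.

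These safeguards are partial. The alert and the contact rule need a reading that nobody has requested. The documents describe no scheduled review of rescue use during the gap. Section 7.3.2.2 resets the FEV1 limit from the Period 2 pre-dose value, so a decline during the gap could lower the reference used afterwards.

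Two comparisons are also offered. FEV1 is unscheduled on many days, but 4.6.1 limits FEV1 to clinic attendance and names PEF as the out-patient measure. PEF is also unscheduled between screening and Day -7, but that is before randomisation, when no stability limit exists.

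**Conclusion.** The point holds as a minor safety-monitoring gap. That no PEF is scheduled between the periods is plain from four places in the two documents. That this falls short of 4.6.1 rests on reading washout as lasting until Period 2 starts, which 4.4 favours but leaves partly open; confidence is medium for that reason.

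The size is 0 days when visits are combined and 27 to 28 days at most, or 56% to 57% of the off-treatment days before Period 2, assuming nominal 14-day treatment with the last dose on Day 14. These figures measure coverage, not risk. The documents give no rate of deterioration and do not say how many subjects will use the gap. The primary FeNO estimate is not called into question.

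**What to change.** Amend the synopsis, Protocol 4.1, Time and Events note 12 and SAP Appendix 3 note 11 so that morning and evening home PEF continues through any gap between Period 1 Day 35 and Period 2 Day 1. Have the site review those readings against the existing 5.4 criteria and the Period 1 PEF limit before the first Period 2 dose. This satisfies 4.6.1 on either reading of washout. Merely defining washout as 21 days would tidy the text but leave the interval without scheduled readings.

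The cost is small. Subjects already have a PEF meter with electronic capture and an alert, so no new device or visit is needed. Section 7 lets the sponsor approve and document added time points without a protocol amendment, so collection can start before the text is aligned. The downside is up to about four more weeks of twice-daily readings for subjects who use the gap.
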